1. ABBREVIATIONS

ADR	Adverse Drug Reaction	IFRA	International Fragrance Association
AE	Adverse Event	IMP	Investigational Medicinal Product
BMI	Body-Mass Index	ITT	Intention-to-Treat
C	Concentration	I/L	Liter
CAS	CAS Registry Number	mg	Milligram
CI	Confidence Interval	mL	Milliliter
CRF	Case Report Form	p.a.	post administrationem
CRO	Contract Research Organization	PTSS	Pre-treatment Sign and Symptom
GCP	Good Clinical Practice	QAU	Quality Assurance Unit
GLP	Good Laboratory Practice	SAE	Serious Adverse Event
GMP	Good Manufacture Practice	SD	Standard Deviation
g	Gramm	SOP	Standard Operating Procedure
ICH	International Conference on Harmonisation of Technical Requirements for Registration of Pharmaceuticals for Human Use	OTC	Over-The-Counter
IEC	Independent Ethics Committee	V	Visit

2. INTRODUCTION

Head lice (*Pediculus humanus capitis*) are parasitic insects that can be found on the head, of humans, particularly school age children. Head lice are tiny, wingless insects (2-3 mm in length) which live among the warmth of human hair, usually close to the scalp, and feed from the blood in the scalp. They crawl but cannot fly or hop. Although small, head lice can be seen with the naked eye. However, a magnifying glass may facilitate observation. When head lice bite the scalp to feed on the blood, it may cause itching; when lice crawl, it can cause a tickling/itching sensation. Lice are also more active in the dark, disrupting the infested person's sleep.

Female lice lay 3-5 eggs (also called nits) per day, which take 1-2 weeks to hatch. Nymphs need 7-10 days to become adult lice. Head lice infest the head and neck and the nits attach to the base on the hair shaft, generally within $\frac{1}{4}$ inch of the scalp. Head lice survive on the human host for up to 30 days.

Lice are spread by direct contact with an infested individual or contact with clothing, worn by the infested individual, or with personal items (e.g., hair brushes, hair ties, towels, bed linens, etc.). Personal hygiene or cleanliness has nothing to do with getting lice. There is no evidence that lice prefer clean or dirty hair or whether the length of the hair increases the risk for being infested with lice. Head lice do not carry diseases, nor can they survive on non-humans (e.g. pets do not transmit). When removed from the human host, head lice usually die within 24 hours. Also, when lice are in water, they become extremely inactive but remain firmly attached to the hair. For this reason, lice are generally not transmitted in the swimming pool; however, sharing the towel, used to dry the hair of the infested individual, may contribute to transmitting head lice.

Head lice are very common; about 10% of the population are infested. From 6 to 12 million infestations occur in the United States each year in children aged 3 to 12 years of age. It occurs more frequently in girls than boys. It occurs less frequently in African Americans than other races; this might be explained by the shape and thickness of the hair shaft.

Diagnosis is made by observing the live louse/lice on the head of the infested individual. Generally, the person looking for live lice and/or nits should use a magnifying lamp. The hair should be divided into small sections to facilitate detection. The areas around the top of the ears and at the neck line are the most common locations for nits [1].

Treatment is recommended if nits are found on the hair. The American Academy of Pediatrics recommends the use of Nix® (1% permethrin) with a second treatment applied 7-10 days later. However, because of increasing resistance and safety concerns with classic treatments, alternative treatments are taking over the European and US markets during the last years, including silicone-based head lice products with a physical mode of action. For some of these products, both *in vitro* and clinical studies have confirmed their mode of action, efficacy and safety [2-5].

3. STUDY RATIONALE

Treatment of head lice infestations remains a clinical relevant problem because of increasing resistance and safety concerns, observed with classic insecticidal pediculicides. For this reason, alternative treatments have been put on the market, relying on a physical mode of action. Some examples are dimethicone- and mineral oil-based products, of which clinical efficacy and safety has been extensively proven [2-5]. Although very efficient, rinseability may be impaired, especially in products containing high molecular weight silicones. For this reason, Oystershell has developed a new water-dispersible, [REDACTED] [REDACTED] head lice treatment (X92001666; Elimax Ultra®; further referred to as "test product"), combining high efficacy (as confirmed by the results of adulticidal and ovicidal experiments) and improved rinseability (and thus user convenience). The test product is classified as medical device and elicits its effect via a physical mode of action (more details are presented in chapter 4.1).

The present study is set-up to compare *in vivo* clinical performance and safety of the test product versus an in the US commercially available, pyrethrum-based product (RID® shampoo). According to US regulations, the rules for clinical trials with drug products and the rules for clinical trials with medical devices must be followed. Before the trial can start, approval according to drug regulation and medical-device regulation must be granted. The study will be performed in subjects ≥2 year of both genders with confirmed diagnosis of head lice infestation. To support safety, local and global tolerability, skin and ocular irritation will be assessed and adverse events (AEs) will be registered.

4. CHARACTERISTICS INVESTIGATIONAL PRODUCTS

4.1. Test product: X92001666 (Elimax Ultra®)

The sponsor will provide test product and the lice comb (OYS internal code: 07080021), which will be incorporated in the final packaging. The site will be providing the Rid Shampoo. The comb will be used following application of either product. The test product X92001666 (Elimax Ultra®) is a medical device for the treatment of head lice infestations. [REDACTED]
[REDACTED]
[REDACTED]
[REDACTED]

[REDACTED]

[REDACTED]

[REDACTED]

[REDACTED]

[REDACTED] acts as a suffocant by penetrating the respiratory system. Consequently, water and gas exchange is impaired, finally resulting in death. In addition, head lice and nits, treated with this product showed severe symptoms of dehydration (in house experiments). Because of its physical mode of action, no resistance is expected to occur.

4.2. Reference product: RID® shampoo

The active ingredient of RID® shampoo, the reference product in this study, is pyrethrum extract (equivalent to 0.33% pyrethrins), combined with piperonyl butoxide (4%). Pyrethrum has been used for centuries as an insecticide and as a lice remedy. This natural insecticide is made from dried flower heads, primarily of *Chrysanthemum cinerariifolium*. The main active ingredients are pyrethrins, also cinerins and jasmolins. Pyrethroids are synthetic, or man-made, versions of pyrethrins, one common example is permethrin. Pyrethrin is usually combined or synergized with piperonyl butoxide. Both chemicals act synergistically to kill lice by acting on nerve cell membranes and interrupting signal travelling between brain and muscles. The lice become paralyzed and die because they are unable to breath.

Pyrethrum has been extensively studied for its effects on people and the environment. Like all insecticides, pyrethrum is used to have a toxic effect on insects. Pyrethrum has a very good toxicity profile. [8]. For mammals, doses that elicit toxic reactions are significantly larger than the exposures people typically experience in using pyrethrum based products.

On broken skin, pyrethrum produces irritation and sensitization, which is further aggravated by sun exposure. Absorption of pyrethrum through the stomach and intestines and through the skin is slow [9]. However, humans can absorb pyrethrum more quickly through the lungs during respiration. Pyrethrum (as 100%) has an acute oral toxicity in rats of LD₅₀ 3500 mg/kg and an acute skin toxicity in rabbits of LD₅₀ 19000 mg/kg [10]. Piperonyl butoxide (as 100%) has an acute oral toxicity in rats of LD₅₀ 6150 mg/kg and an acute skin toxicity in rabbits of LD₅₀ 1880 mg/kg.

Response appears to depend on the pyrethrum compound used. Inhaling high levels of pyrethrum may bring about asthmatic breathing, sneezing, nasal stuffiness, headache, nausea, lack of coordination, tremors, convulsions, facial flushing and swelling, and burning and itching sensations [10]. The lowest lethal oral dose of pyrethrum is 750 mg/kg for children and 1000 mg/kg for adults [11]. At high doses, pyrethrum can be damaging to the central nervous system and the immune system [12].

Pyrethrins and their metabolites are not known to be stored in the body nor excreted in the milk. The urine and feces of people given oral doses of pyrethrum contain chrysanthemumic acid and other metabolites [13]. In mammals, tissue accumulation has not been recorded.

Overall, pyrethrins have low chronic toxicity to humans and the most common problems in humans have resulted from the allergenic properties of pyrethrum. Pyrethrum can produce skin irritation, itching,

pricking sensations and local burning sensations [10]. Pyrethrins appear to have low reproductive toxicity [14].

5. OBJECTIVES & ENDPOINTS

5.1. Primary objective

The primary objective of this study is to demonstrate that the cure rate after local application of test product is better than a predefined limit. The test product must achieve a cure rate superior to 70% (at the end of day 10, corrected for re-infestation).

To compare efficacy and safety of test product against reference product in subjects, infested with head lice (*Pediculus humanus capitis*).

5.2. Secondary objectives

Secondary objectives refer to comparison of the cure rate of test product with those of reference product using the following endpoints:

Secondary efficacy objectives:

- a) To show that the cure rate at the end of day 10 (corrected for re-infestation) for the reference product for all baseline infestations is better than 70%.
- b) To show that the test product has a cure rate superior to that of the reference product.
- c) In case that superiority cannot be shown: to show that the test product is non-inferior to reference product regarding cure rate. A non-inferiority margin of 7.5% will be used.

Further secondary objectives refer to objectives c and d, however evaluated in subgroups or other time points.

- d) Efficacy of the investigational products for head lice for mild and moderate baseline infestations (cure rate at the end of the study day 10, corrected for re-infestation).
- e) Efficacy of the investigational products for head lice for all baseline infestations (cure rate at day 1).
- f) Efficacy of the investigational products for head lice for mild and moderate baseline infestations (cure rate at day 1).

As further secondary objectives, safety and tolerability of test product or reference as well as the acceptance of the investigational products will be evaluated.

Secondary safety objectives;

- g) To evaluate local tolerability by subject: subjective symptoms (burning, paraesthesia, pruritus): 0h, 1h, 24h, 7d and 10d p.a. (descriptive evaluation).
- h) To evaluate global tolerability by the subject and study staff (number of subjects with global tolerability ratings of “very good”, “good”, “moderate”, “poor”, descriptive evaluation) at 10d

after application.

- i) To evaluate skin irritation by study staff (secondary infection, erythema, excoriation) on day 0, 1, 7 and 10.
- j) To evaluate eye irritation by study staff on day 0, 1, 7 and 10.
- k) To evaluate characterization of safety and tolerability of the investigational products considering Adverse Events in the study population.

5.3. Endpoints

The primary endpoint is the cure rate at the end of day 10 (corrected for re-infestation) for the test product for all baseline infestations.

The secondary endpoint is the difference of cure rates (as defined as primary endpoints) between both treatments.

Safety endpoints are the secondary characteristics of the lice infestation (see Section 9.4) and reported adverse events.

6. INVESTIGATIONAL PLAN

6.1. Study Design

This dual-centre, randomized, controlled, investigator-blinded, comparative study will be conducted in 70 subjects (male and female subjects; age ≥ 2) with confirmed diagnosis of head lice infestation. All subjects will be randomized in a 1:1 ratio in both treatment groups.

In this study, a repeated treatment will be performed, as described in the literature. For two-treatment protocols, it is recommended that the second treatment should be applied on day 7 to day 8 and the final assessment should be on day 10 [15]. In total, 4 visits are planned:

- Visit 1 – Baseline visit (Day 0; first treatment)
- Visit 2 – Post treatment evaluation visit (Day 1: 24hrs +/- 3 hrs.)
- Visit 3 – 2nd treatment visit/evaluation (Day 7 + 1 day)
- Visit 4 – Final evaluation visit (Day 10 + 2 days)

Subjects complying with the in- and exclusion criteria will receive the study medication according to a subject number, allocated in ascending order in correspondence with their inclusion into the study. Both investigational products will be tested as described in the product leaflets in compliance with the above-mentioned treatment recommendations.

6.2. Screening/Treatment Day (Day 0)

Subjects with suspicion of head lice infestation will be recruited for this study. Written informed consent will be obtained from adult subjects or the legal representative of minors. Children, must give their assent in written. The assent of younger children will be given verbally as far as appropriate. Subject's eligibility for participation in the trial will be established by the investigator prior to enrolment. Screening assessments will include recording of demographic data, medical history and current medication usage, an assessment of the head, scalp and eyes, vital signs, and a urine pregnancy test in females of child-bearing potential. A subject must meet all inclusion criteria, and none of the exclusion criteria, to be eligible.

Diagnosis of a head lice infestation will be confirmed by identification of at least five living adult head lice or nymphs and five apparently live eggs. The severity of the infestation will be judged on a 4-point severity scale:

- 0 = no relevant infestation (0-4 lice and/or nymph present)
- 1 = mild (5-9 lice and/or nymphs present)
- 2 = moderate (10-24 lice and/or nymphs present)
- 3 = severe (≥ 25 lice and/or nymphs present)

Subjects who meet the inclusion criteria will be randomized to receive test product or reference product. Prior to the study, a block randomisation (block sizes of 2) will be performed by the external statistician using statistical software (R version 3.4.2; R-development core team, 2017). The randomization schedule will be send to the sites prior to study conduct. All subjects will be enrolled into the study sequentially beginning with Subject Number 1-70.

Following the instructions for use, subjects will have the test product applied by clinic personnel to ensure consistent application and consequently combed with a lice comb (also see chapter 7). Date and times of start and end of application of the investigational product and times of tolerability and efficacy assessments will be documented. Post-treatment assessments will be performed directly after start of treatment, as well as 1 hour after removing the investigational product. This will be considered Day 0 of the study.

If household members exhibit infestation with lice or nits, they will be offered the opportunity to participate in the study or will receive the standard of care if they choose not to participate in the study. In addition, household members will be advised to wash bed linens, towels, and brushes or combs used on the hair to prevent reinfestation.

To sum up, at visit 1, the following operations will be performed and/or parameters controlled by the study team:

- Age-appropriate subject information and obtaining of written informed consent
- Documentation of demographic data
- Documentation of medical history
- Documentation of pre-existing or concomitant medication
- Verifying of head lice infestation, incl. severity

- Checking of inclusion and exclusion criteria including pregnancy test if applicable
- Decision regarding study inclusion, randomisation
- Baseline assessments (including local tolerability before treatment)
- First application of the investigational product

- Post-treatment assessments (local tolerability, skin and eye irritation, adverse events) directly after start of treatment, as well as 1 hour after removing the investigational product
- Questionnaire on the satisfaction with esthetical effect of the products

After the assessments, the subject is released from the clinical ward and advised to follow the instructions / restrictions made in the protocol and to come back on the next day for the second visit.

6.3. Evaluation Visit (24 ± 3 hours)

24 hours (± 3 h) after end of study drug administration, the subjects will attend the study site. After the 24-hour interval, the clinical evaluator will perform the efficacy and tolerability assessments.

These data, any concomitant medication taken during the study period, adverse events and any change in concomitant diseases will be recorded in the Case Report Form (CRF). Therefore, at visit 2 the following operations will be performed:

- Hair scalp assessment for living lice (all stages) by study staff (see chapter 9.4.8)
- Assessments of skin and eyes irritation, local tolerability
- Questioning on general well-being
- Registration and documentation of any adverse event and/or changes regarding concomitant diseases, concomitant medication, withdrawal criteria
- Vital signs

In case that the examination of the hair and scalp (diagnostic combing; see chapter 9.4.8) will show active head lice infestation, the life stage of the lice will be documented. Subject will not be removed from the study and will continue until study end.

6.4. Second Treatment (Day 7 + 1 day)

On study day 7 (+1 day), the scalp and hair will be examined for live head lice by blinded study staff. The life stage of the lice will be documented. The assessments of skin and eyes irritation will be performed within 1h prior to administration. Subjects without severe skin or eyes irritations will receive a second treatment with the assigned test product. The subjects will be asked for any concomitant medication taken during the study period and adverse events that occurred.

At visit 3 the following operations are being performed by the study team:

- Hair scalp assessment for living lice (all stages) by study staff (see chapter 9.4.8)
- Second application of the investigational products by the study staff
- Assessments of skin and eyes irritation, local tolerability
- Questioning on well-being
- Registration and documentation of any adverse events and/or changes regarding concomitant diseases, concomitant medication, withdrawal criteria
- Vital signs

6.5. Final evaluation visit (Day 10 + 2 days)

The final visit will be performed on study day 10 (+2 days). The final visit examination is performed to verify if the subject is cured. A subject will be considered cured, if no living head lice could be detected. If living lice present on day 10, the life stages of the lice will be documented. If any other pediculicidal agents was employed during the observation period, the subject will be considered a treatment failure (no efficacy analysis will be performed).

The following examinations will be performed within the final visit:

- Hair scalp assessment for living lice (all stages) by study staff (see chapter 9.4.8)
- Assessments of skin and eyes irritation, global tolerability, local tolerability
- Questioning on well-being
- Registration and documentation of any adverse events and/or changes regarding concomitant diseases, concomitant medication, withdrawal criteria
- Questionnaire on the satisfaction with the esthetical effect of the products
- Vital signs

In case that the examination (diagnostic combing) will show active head lice infestation (living nymph or imago), the subject will be considered treatment failure or re-infestation and will receive the standard of care at the site.

Subjects exhibiting either subjective or objective abnormalities when the trial has been completed will be followed up. Any AE which remains unresolved after completion of the trial requires detailed evaluation and follow-up until the AE has been resolved or a reasonable explanation for its persistence is found. If the subject refuses to follow the instructions of the study staff, the latter is released from responsibility.

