6.6. Restrictions

- No parallel use of any other anti-head lice therapy.
- Subject agrees not to cut or chemically treat their hair while participating in the study
- Female subjects are to be informed that they must apply adequate contraceptive methods (e.g. uterine tube sterilization, sexual abstinence or vasectomized partner or combination of anti-conceptive medication and condom, spermicidal products, diaphragm, temperature method).
- Subjects agree not to use any other anti-lice treatment for the duration of the study.

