8.4. Removal of volunteers from treatment or assessment

8.4.1. Withdrawal criteria

- Serious Adverse Events (SAE's)
- Diseases requiring treatment that occur during the study, which do not constitute SAE's but which, in the opinion of the Principal Investigator, would probably prevent achievement of the study objectives.
- Non-adherence to the study conditions or relevant deviations from procedures as established in the study protocol.
- Withdrawal of consent.
- Duration of treatment < 15 minutes for test product or < 10 minutes for reference product.
- Severe irritation of the skin or the eyes on pre-treatment assessment on day 7.
- Use of any other anti-head lice therapy.

All details and reasons for removal of trial subjects from the study will be recorded in the study termination section of the Case Report Form (CRF). CRFs of all trial subjects entered into the study must be kept in the documentation of the study. Reasons for withdrawal of trial subjects will be entered into the final report of the study. Every effort must be made to follow-up trial subjects who terminate with drug-related AE's to determine the final outcome.

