8.5. Intention-to-treat (ITT) and Safety population

The safety set/population consists of all subjects who were randomised and exposed to study medication.

The ITT population contains any subject included and randomized in the study, with available baseline value of the primary endpoint and at least one follow-up visit for the efficacy parameters.

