9.6. Prior and concomitant therapy

Topical use of medication on scalp and hair, prior to the first intended administration of the investigational products, which is listed in the exclusion criteria (see section 8.6.1), will prevent inclusion into the study.

Treatment of a previous anti-lice treatment with exception of combing the hair using a lice comb within 30 days will prevent inclusion into the study. Treatment with an anti-lice treatment during the study will lead to exclusion of the subject.

Any pre-existing chronic medication taken for treatment of existing disorders and not considered to interfere with the study course or to influence scalp healing will be allowed.

Intake of pre-existing chronic medication used by the subject should be continued throughout the study at a conventional dose and schedule. Their use is to be recorded in the CRF and medical records.

Checks for concomitant medication will be performed at all study visits.

If a subject needs concomitant medication during the study, the responsible investigator should be asked. Concomitant medication is to be documented by brand, type (generic name, if applicable), amount and duration on the CRF. The Principal Investigator / investigator will then decide together with the responsible project manager of the study center, whether the subject must be excluded.

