10.4. Efficacy Analyses

Efficacy analyses will be performed on the ITT population, consisting of all subjects who were included and randomized in the study, with available baseline value of the primary endpoint and at least one follow-up visit for the efficacy parameters. All statistical test will be performed at a 5% level of significance.

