10.4.1. Analysis of primary objective

The cure rate (p) corresponds to the proportion of subjects who are cured at day 10 among all subjects that received any treatment at day 0. The aim of the study is to show superiority for the cure rate of the test product versus a predefined limit of 70%.

The following null hypothesis will be tested:

$$H_{0, \text{prim}}: p_T - p_R = 0 \text{ and } H_a: p_T - p_R > 15\%$$

A χ^2 -test of independence will be used to test the null hypothesis.

In case superiority could not be proven, non-inferiority will be tested. According to ICH guideline “Points to consider on switching between superiority and non-inferiority” [17], it is allowed to assess non-inferiority in to the absence of superiority. Prerequisites include:

- predefinition of a non-inferiority margin
- no correction in terms of multiplicity

As non-inferiority margin (δ), a 7.5% worse cure rate is regarded as clinically not relevant. The following null hypothesis will be used: $H_{0, \text{NI}}: p_T - p_R < \delta$, whereby $\delta = -7.5\%$. The lower, 95% confidence interval (CI) of the difference $p_T - p_R$ will be used for the test. If $H_{0, \text{NI}}$ will be rejected, non-inferiority cannot be shown.

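### Section 6.5 scores a user of another pediculicide as a failure yet says no efficacy analysis follows; separately, the ITT set (8.5, 10.4) and the 10.4.1 denominator differ

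*Combined protocol and SAP*

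**What the plan says.** **Users of another pediculicide.** Section 6.5 says of such a subject that "the subject will be considered a treatment failure (no efficacy analysis will be performed"; the bracket closes there. Three other sections bear on the same subject:

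- 8.4.1 lists "Use of any other anti-head lice therapy" among the withdrawal criteria.
- 9.6 states: "Treatment with an anti-lice treatment during the study will lead to exclusion of the subject".
- 8.4.2 sends a drop-out's data, other than adverse events, to individual listings in an appendix of the report.

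**Analysis set and denominator.** Section 10.4 states that "Efficacy analyses will be performed on the ITT population". Section 8.5 defines that population as randomised subjects "with available baseline value of the primary endpoint and at least one follow-up visit for the efficacy parameters", and 10.4 repeats the definition. Section 10.4.1 defines the cure rate as "the proportion of subjects who are cured at day 10 among all subjects that received any treatment at day 0". None of these three sections excludes users of another product. Section 10 gives no rule for a missing Day 10 result.

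**Context.** Section 6.6 prohibits such use: "No parallel use of any other anti-head lice therapy". Section 6.3 says of a subject with live lice on Day 1: "Subject will not be removed from the study and will continue until study end". Section 6.4 places the next application on Day 7 (+1 day).

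**The concern.** The primary objective in 5.1 is a cure rate above 70% for the test product. A subject scored as a failure belongs in the denominator; a subject with no efficacy analysis does not. Section 6.5 says both of one subject. Two statisticians following this plan could report different primary cure rates from the same data.

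The second mismatch does not depend on 6.5. A subject treated on Day 0 who never returns has no follow-up visit, so 8.5 and 10.4 leave that subject out. Section 10.4.1, read as written, keeps the subject in the denominator, and a subject never examined on Day 10 cannot be counted as cured.

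Other lice treatment is prohibited, so users may be few, and the documents give no rate for users or for non-returners. It is plausible that someone with live lice after Day 1 would turn to another product before Day 7, which would link the removals to failure. That link is an inference; the documents do not state it.

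**Working it through.** **1. The sections side by side**

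| Subject | 6.5, read literally | ITT set (8.5, 10.4) | 10.4.1 denominator |
|---|---|---|---|
| Treated Day 0, returned at least once, used another product | Failure, but no efficacy analysis | In | In |
| Treated Day 0, never returned | Not addressed | Out | In |

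**2. Inputs**

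The limit of 70% comes from 5.1 and 10.4.1, and 35 per arm from 8.1 (10.1 and 10.2 give 30). The planned 95% and 55% come from 8.1 and 10.2. The plan has no figure for this point to reproduce. It names no test against 70%, since 10.4.1 writes its hypothesis as a difference between arms, and 10.4 gives a 5% level without sidedness. The one-sided exact binomial test and all counts of users or non-returners below are therefore assumptions.

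**3. Direction within one arm**

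With c cured of n, removing k subjects counted as not cured changes c/n to c/(n − k), which is never smaller.

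**4. How many subjects matter near the boundary**

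p = Σ (x = c to n) C(n, x) · 0.7^x · 0.3^(n − x)

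- One-sided 5%: 29/35 = 82.9%, p = 0.065; 29/34 = 85.3%, p = 0.033. The cures needed are 30 of 35 or 29 of 34.
- One-sided 2.5%: 30/35 = 85.7%, p = 0.027; 30/34 = 88.2%, p = 0.012. The cures needed are 31 of 35 or 30 of 34.

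At either level, one subject can decide a result that lies at the boundary. The arithmetic is the same for a user of another product and for a subject who never returns.

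**5. Chance of the claim of more than 70%** (35 in the arm, one-sided 5%, critical value recomputed for each analysed n)

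First, let each subject not cured be removed independently with probability f:

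| f | True rate 70% | True rate 95% |
|---|---|---|
| 0 | 2.7% | 99.3% |
| 0.1 | 5.6% | 99.6% |
| 0.2 | 9.3% | 99.8% |
| 0.3 | 14.9% | 99.9% |

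Second, suppose that 95% applies only to the other subjects and that k of the 35 are users or non-returners:

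| k | Counted as not cured | Removed |
|---|---|---|
| 1 | 97.4% | 99.4% |
| 2 | 91.9% | 99.5% |
| 3 | 78.6% | 98.0% |

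**6. Between arms** (assumed counts, 35 per arm, uncorrected chi-square)

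- 29 versus 19 cured, with 1 and 6 users: counted as failures, 29/35 − 19/35 = 28.6 points (p = 0.010); removed, 29/34 − 19/29 = 19.8 points (p = 0.066).
- 31 versus 19 cured, with 2 and 2 users: counted, 31/35 − 19/35 = 34.3 points (p = 0.0015); removed, 31/33 − 19/33 = 36.4 points (p = 0.0006).

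Removal shrinks the difference in the first case and widens it in the second.

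**The case against.** The main clause of 6.5 fixes the outcome as failure, and that label has meaning only within an efficacy analysis. The bracketed remark may then say no more than that the Day 10 examination is not used, because the result is already determined. Sections 8.5, 10.4 and 10.4.1 contain no exclusion for such users, so reading them together keeps the user as a failure. This stands as a plausible reading and limits confidence in the first part. It does not close the question: the text does not say so, and 8.4.1, 8.4.2 and 9.6 can be read towards removal.

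On the second part, 10.4.1 sits under 10.4, so its denominator could be read as falling within the ITT set. The first follow-up is also only 24 hours after treatment, so non-returners may be rare. Both remarks are fair, but the two definitions still differ as written, and only one of them has a follow-up condition.

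On size, about 0.95 × 35 = 33 cures are expected under the plan against 30 needed, so a result at the boundary is not the planned case. That also stands.

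A reader might infer that the plan deliberately discards failures, or that removal favours the test product over the reference. The documents support neither. The first rests on one ambiguous bracket, and the second depends on how the removed subjects divide between the arms.

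**Conclusion.** The point holds in two parts. The contradiction within 6.5 is real text with a possible harmless reading (medium confidence). The mismatch between the ITT set and the 10.4.1 denominator is plain from the definitions (high confidence). Both should be fixed before data are seen.

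Within an arm, dropping these subjects rather than counting them as not cured can only raise the cure rate or leave it unchanged, which favours the claim of more than 70%. The size depends on assumptions. One subject can decide a result near the boundary (29/35, p = 0.065; 29/34, p = 0.033; one-sided exact test at 5%). If 95% is the overall cure rate, the effect is negligible: 99.3% versus 99.8% with a fifth of failures removed. The larger effects in the working need either a true rate near 70% or several users or non-returners on top of the planned 5% of failures, and the documents give no rate for either group. No direction is claimed for the comparison between arms.

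**What to change.** - In 6.5, delete the bracketed remark and keep the classification as a treatment failure.
- Make the 10.4.1 denominator, meaning all randomised subjects treated on Day 0, the single primary efficacy set, and align 8.5 and 10.4 with it.
- In 8.4.1, 8.4.2 and 9.6, state that withdrawal, drop-out or exclusion does not remove a subject from that denominator. The final evaluation sought in 19.1 and all subject management stay as they are.
- In 10.4.1, count as not cured any subject who used another pediculicide before the Day 10 assessment and any subject with no Day 10 assessment. An observed-case sensitivity analysis is optional.

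The cost is wording only. Section 6.7 already has restrictions checked on Days 1, 7 and 10, so no new data are needed. The downside is that the reported cure rate may be slightly lower.
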